#### **INTERVENTIONS**

**Presentation:** The outreach presentation will last 75 minutes with an additional 15 minutes for caregiver questions. The presentations will occur in the evening via Zoom. The presentation will include information about identifying anxiety disorders, strategies for caregivers to help their youth with anxiety, evidence-based practices to treat youth anxiety, and strategies for finding a therapist who uses cognitive behavior therapy with exposures. The text on the presentations is written at a 5.3 grade reading level. Presentations will incorporate stigma reduction strategies, such as education to dispel myths, and behavioral decision-making tools to elicit hope, empowerment, and motivation.

**Researcher-Only condition:** The researcher-facilitated presentation, led by two clinical psychology graduate students, will be the same for all schools.

**Key opinion leader:** The key opinion leader (KOL) co-facilitated presentations will include the same core principles as the researcher-facilitated presentation but may vary by school in terms of specific examples and content emphasized based on KOL feedback. A caregiver KOL from the local community will co-facilitate the presentation with a clinical psychology graduate researcher. To select the KOLs, the principal investigator will contact the school PTA (or a similar parent group), and PTAs will be asked, "please nominate a caregiver who is well-known and respected within your community, and who reflects the diversity of the school as a whole." The PI will meet with the KOLs to review the presentation and to engage them in championing cognitive behavior therapy for youth anxiety.

## **MEASURES**

#### Primary outcome measure:

1. Change From Pre-Presentation to Post-Presentation in Treatment Seeking Evaluation - Intention to Seek Cognitive Behavioral Therapy [Time Frame: pre-presentation; post-presentation (within 1 week after the presentation)]

Participants rate how likely they are to seek a therapist who uses exposure therapy for their child in the next three months on a scale ranging from 1 (*very unlikely*) to 5 (*very likely*).

2. Number of Participants Who Sought Cognitive Behavioral Therapy as Assessed by Treatment Seeking Evaluation - Actual Cognitive Behavioral Therapy Seeking [Time Frame: 3-month follow-up]

Participants indicate whether they sought exposure therapy for their child since the presentation (yes/no).

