## **Primary Aims**

**Aim 1:** Test the relative effects of researcher-only and KOL conditions on changing caregivers' intention to seek CBT for their youth, and actual CBT seeking at three-month follow up.

*Hypothesis 1a:* Relative to the researcher-only condition, the KOL condition will result in a greater increase in intention to seek CBT with exposures.

*Hypothesis 1b:* Relative to the researcher-only condition, the KOL condition will result in a greater seeking of CBT with exposures for their youth at the three-month follow-up.

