#### **PARTICIPANTS**

#### Criteria for inclusion:

- Be least 18 years of age
- Be fluent in English
- Be the primary caregiver of a youth aged 5 to 18 years
- Have a child at one of the schools offering a presentation

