#### Criteria for exclusion:

None

**Sample size:** For aim 1 and 3, a Monte Carlo-based power estimate was derived using Mplus with 10,000 replications. For the sample size of 180, assuming a Type I error rate of 5%, a two-tailed test, statistical power was .83 to detect a medium-sized effect (r = .30) of randomization group on longitudinal changes, given an expectation of a small (r = .15) effect for the control group. For aim 2, power was calculated using G\*Power. Given the brevity of the three-month follow-up questionnaire, a 10% attrition rate was assumed. Assuming a Type I error rate of 5%,

a two-tailed test, and a 25% rate of seeking EBPs in the researcher-only condition, statistical power was .82 to detect a medium effect (odd ratio = 1.72).

**Randomization:** Participants will be cluster randomized by school using restricted randomization with Excel's random number generator.

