### **Exploratory outcome measures:**

- 7. Change From Pre-Presentation to Post-Presentation in Barriers to Seeking Treatment [Time Frame: pre-presentation; post-presentation (within 1 week after the presentation)]

  The Barriers to Seeking Treatment questionnaire asks participants to indicate whether they agree with 21 potential barriers to treatment (Heeringa et al., 2004). A count of the total number of barriers will be used in analyses.
- 8. Change From Pre-Presentation to 3-Month Follow-Up in Barriers to Seeking Treatment [Time Frame: pre-presentation; 3-month follow-up]

The Barriers to Seeking Treatment questionnaire asks participants to indicate whether they agree with 21 potential barriers to treatment (yes/no; Heeringa et al., 2004). A count of the total number of barriers will be used in analyses.

9. Client Satisfaction Questionnaire [Time Frame: post-presentation (within 1 week after the presentation)]

The Client Satisfaction Questionnaire assesses participants' satisfaction with the presentation. Items are rated on scale ranging from 1 to 4. Items are summed; higher composite scores indicate greater program satisfaction.

10. Relatability Evaluation [Time Frame: post-presentation (within 1 week after the presentation)]

The Relatability Evaluation will be used to evaluate participants' impression of the presenter. Participants will rate each presenter (scale ranging from 1 to 5) on 10 items associated with aspects of key opinion leaders: relatable, likeable, similar, think similarly, similar beliefs, credible, trustworthy, understanding of the local community, familiar, and friendship. Items are summed; higher composite scores indicate that the presenter is more relatable.

11. Brief Revised Child Anxiety and Depression Scale-Parent Version [Time Frame: prepresentation]

The total anxiety scale (15 items) from the Brief Revised Child Anxiety and Depression Scale-Parent Version will be used to assess youth anxiety (Ebesutani et al., 2017). Participants rate items on a scale from 0 (*never*) to 3 (*always*). Items are summed; higher scores indicate higher levels of anxiety.

12. Demographics [Time Frame: pre-presentation]

A demographics questionnaire will assess caregiver and youth age, gender, race, ethnicity, and nativity; caregiver level of education, income, and religion; and youth health insurance status.

13. Content Checklist [Time Frame: during the 1.5 hour presentation]

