A content checklist will assess the core components of the presentation, as well as presenter and audience member self-disclosure about experiencing receiving therapy for themselves or their child (yes/no). Self-disclosure will be considered to have been made if either the presenter or an audience member self-discloses about their experiences.

14. Qualitative Interview [Time Frame: 3-month follow-up]

A qualitative interview will ask participants about the following topics: (1) their perception of presenters; (2) ways in which the presenters affected their decision to seek treatment; (3) factors they considered when seeking treatment; (4) strategies they have used from the presentation; (5) their perception of exposure therapy; and (6) general ways that the mental health system could be improved to improve access to therapy.

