researcher co-facilitator) as a person-level predictor; and time (pre- and post-presentation) as an observation-level predictor. In separate multilevel models, (a) intention to seek CBT, (b) Therapy Subjective Norms Questionnaire—CBT, (c) Caregiver Attitudes about CBT, (d) Parents' Internalized Stigma of Mental Illness Scale, and (e) Parent Engagement in Evidence-Based Services Questionnaire-Knowledge subscale will be regressed on time, condition, and the interaction between time and condition; a random intercept will be included in all five multilevel models. A binary logistic regression will be conducted with CBT service seeking at the threemonth follow-up (Treatment Seeking Evaluation - Actual CBT seeking) entered as the dependent variable, condition entered as the independent variable, and youth anxiety (Brief Revised Child Anxiety and Depression Scale-Total Anxiety) entered as a control variable. Ttests will be used to compare difference between conditions for each item on the Relatability Evaluation of the principal investigator. This study will examine caregiver demographic factors, youth anxiety (Brief Revised Child Anxiety and Depression Scale-Total Anxiety), racial similarity to the presenter (Demographics, same race), and self-disclosure (Content Checklist, selfdisclosure), as potential moderators of the effect of presentation condition on intention to seek CBT. In separate multilevel models, intention to seek CBT will be regressed on time, condition, each potential moderators, and their three-way interaction.

**Qualitative Analyses:** The transcribed qualitative interviews will be entered into NVivo software for analysis. Qualitative analyses will use a direct content analysis approach (Hsieh & Shannon, 2016). The coding team will create an initial codebook using the primary topics asked in the qualitative interviews. Additional codes will be added to code text that does not fit into the initial categories, either to split the initial codes into two, or to create new codes. Coding will occur through a consensus process in which each transcript will be coded independently by two raters, who will arrive at consensus through discussion (Hill et al., 2005). Thematic responses will be examined by both condition and by whether the caregiver has sought treatment for their youth (4 groups total).

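### No listed baseline measure records exposure-therapy status, and the plan does not say how families already in or awaiting treatment count in the CBT-seeking outcome

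*Combined protocol and SAP*

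**What the plan says.** All references are to the Combined protocol and SAP.

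- **Eligibility.** A participant must "Be the primary caregiver of a youth aged 5 to 18 years", and must also be an adult, speak English fluently and have a child at a participating school. Nothing concerns treatment. Under "Criteria for exclusion" the plan lists none.
- **Outcome.** Primary outcome 2 reads "Participants indicate whether they sought exposure therapy for their child since the presentation (yes/no". Hypothesis 1b, in Primary Aims, is a comparison of two presentation formats: "Relative to the researcher-only condition, the KOL condition will result in a greater seeking of CBT with exposures for their youth at the three-month follow-up".
- **Baseline measures.** The demographics entry, in Exploratory outcome measures, ends with "caregiver level of education, income, and religion; and youth health insurance status". Neither it nor any other listed pre-presentation measure covers current, scheduled or wait-listed therapy. The content checklist touches on therapy experience, but for the session as a whole: "Self-disclosure will be considered to have been made if either the presenter or an audience member self-discloses about their experiences".
- **Model.** Planned Analyses specifies a logistic regression on condition, with youth anxiety "entered as a control variable". There is no other covariate.
- **Allocation.** "Participants will be cluster randomized by school using restricted randomization with Excel's random number generator". The number of schools and the factors used for the restriction are not given.
- **Timing.** At the SAP date 17 participants had pre/post data, no three-month data existed and nothing had been analysed.

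**The concern.** Outcome 2 has no baseline counterpart. A caregiver whose child is in exposure therapy, or has a place arranged, has little scope to start seeking it. At three months that caregiver could reasonably answer no (nothing new was sought) or yes (the child continues, changes therapist, or has reached the top of a list joined before the presentation). Neither answer need reflect demand created by the presentation, and the plan gives no rule for choosing between them.

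Three things are at stake:

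- Families who answer the same way in both arms dilute the contrast.
- Inconsistent answers misclassify the outcome. This carries into the qualitative comparison, which also groups caregivers by whether treatment was sought.
- Schools are the randomized unit, so the share already in treatment can differ between arms by chance. Without the item, nobody can see that or adjust for it.

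A related gap is that the eligibility criteria, the anxiety scale, the intention item and the seeking item are not tied to one child. A caregiver of several children could rate anxiety for one and report seeking for another.

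**Working it through.** **1. The plan's own figure.** The Sample size section gives 25% seeking in the researcher-only arm, an odds ratio (OR) of 1.72, two-sided 5%, 10% attrition and power .82. Taking N = 180 and assuming 1:1 allocation, 180 × 0.9 / 2 = 81 per arm.

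- KOL-arm rate: odds = (0.25/0.75) × 1.72 = 0.5733, so p2 = 0.5733/1.5733 = 0.3644. The difference is 11.4 points.
- Power = Φ[(p2 − p1 − 1.96 × SE0)/SE1], with SE0 = √(2 × p̄(1 − p̄)/n) and SE1 = √((p1(1 − p1) + p2(1 − p2))/n).
- With p̄ = 0.3072 and n = 81, SE0 = 0.0725 and SE1 = 0.0719, so power = Φ[(0.1144 − 0.1421)/0.0719] = Φ(−0.385) = 0.35.

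The stated .82 is not reproduced for a two-group condition. That is a separate and larger issue. Here 0.35 serves only as the reference for relative change. Clustering is ignored throughout.

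**2. Dilution with equal shares.** Let q be the share already in, scheduled for or wait-listed for exposure therapy. The documents do not give q, so it is varied over 10, 20 and 30%. Assume 25% and 36.4% apply to everyone else. Arm rate = (1 − q) × p + q × y, where y = 0 if these families all answer no and y = 1 if they all answer yes. The risk difference is (1 − q) × 11.4 points in both cases.

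| q | Risk difference (points) | Rates, all no | OR | Power | Rates, all yes | OR | Power | Power, families left out |
|---|---|---|---|---|---|---|---|---|
| 0% | 11.4 | 25.0 vs 36.4% | 1.72 | 0.35 | 25.0 vs 36.4% | 1.72 | 0.35 | 0.35 |
| 10% | 10.3 | 22.5 vs 32.8% | 1.68 | 0.31 | 32.5 vs 42.8% | 1.55 | 0.27 | 0.32 |
| 20% | 9.2 | 20.0 vs 29.2% | 1.65 | 0.27 | 40.0 vs 49.2% | 1.45 | 0.21 | 0.29 |
| 30% | 8.0 | 17.5 vs 25.5% | 1.61 | 0.24 | 47.5 vs 55.5% | 1.38 | 0.17 | 0.26 |

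Example (q = 20%, all yes): 0.2 + 0.8 × 0.25 = 0.400; 0.2 + 0.8 × 0.3644 = 0.4915; OR = (0.4915/0.5085)/(0.400/0.600) = 1.45.

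At an effect large enough for power of 0.808 with 81 per arm (OR 2.57), power falls to 0.742, 0.668, 0.587 (all no) or 0.692, 0.578, 0.473 (all yes). With these families left out it is 0.765, 0.715, 0.656.

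**3. No true effect.** With equal q, both arms have the same rate and the OR is 1.00. With 10% in the researcher-only arm, 20% in the KOL arm, and 25% seeking among the rest of both:

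- All yes: 0.10 + 0.90 × 0.25 = 32.5% and 0.20 + 0.80 × 0.25 = 40.0%, a difference of +7.5 points, OR 1.38.
- All no: 0.90 × 0.25 = 22.5% and 0.80 × 0.25 = 20.0%, a difference of −2.5 points, OR 0.86.

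**4. How unusual that imbalance is.** With 81 independent caregivers per arm, the standard error of the difference in q is √((0.10 × 0.90 + 0.20 × 0.80)/81) = 0.0556. Ten points is then 1.8 standard errors (two-sided p about 0.07). If treatment clusters by school it is more likely. How much more cannot be worked out without the number of schools.

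**The case against.** The case against is substantial, and most of it stands.

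- **A reader might infer that the outcome mixes earlier treatment with new seeking.** The wording does not support that. The item is restricted to the time after the presentation, so a family that sought nothing new should answer no. What remains is ambiguity about continuing, switching or waiting-list families, and reporting error.
- **A reader might infer that the trial cannot isolate its effect.** Both arms receive a presentation and the hypothesis compares them. Randomization balances earlier treatment in expectation, and chance imbalance in an unmeasured factor is already allowed for by a valid test. Families with little scope to seek also belong to the audience that a school talk reaches.
- **The 25% and OR 1.72 are stated for whole arms**, so any dilution may already be in them. This stands: the table is conditional and does not correct the plan's inputs. On the whole-arm reading with q = 20% all answering no, the rest would need 0.25/0.8 = 31.3% versus 0.3644/0.8 = 45.6%, an OR of 1.84.
- **The gain is small where families answer as the item is worded.** At OR 1.72, power is 0.31, 0.27, 0.24 with them included and 0.32, 0.29, 0.26 with them left out.
- **Hypothesis 1a is little affected.** It is tested on pre-to-post change, so a stable low rating attenuates change at most.
- **A reader might infer that status is never collected, or could not be recovered later.** The questionnaires are not reproduced, so an unlisted item cannot be ruled out, and a retrospective question is possible though weaker.

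The objection does not remove the missing coding rule, or the inability to see or adjust for an imbalance between schools.

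**Conclusion.** The point holds as a low-cost improvement to a primary outcome. It does not show an error in the plan or a biased comparison.

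The effect on the odds ratio ranges from slight (1.72 to 1.61 at worst, all no) to material (1.72 to 1.38 at worst, all yes). Actual answers would probably lie between the two. A 10% versus 20% imbalance under no true effect gives an OR between 0.86 and 1.38.

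These sizes rest on assumed shares of 10 to 30%, on OR 1.72 holding among the other caregivers, on 1:1 allocation with 81 per arm for power, and on no clustering. Unbiasedness in expectation also assumes that who signs up within a school does not depend on its allocated condition. The plan does not discuss this.

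**What to change.** 1. **Baseline item.** Add to the pre-presentation questionnaire: *Is this child now receiving, or already scheduled or wait-listed for, CBT with exposures? (yes/no)*
2. **Index child.** Tie this item, the anxiety scale, the intention item and the follow-up item to one named child per caregiver.
3. **Coding rule.** State in the follow-up item that care in place or arranged before the presentation is coded as not newly sought. Also state how a change of exposure therapist is coded.
4. **Primary H1b analysis.** Keep every participant, with baseline status as a prespecified covariate beside youth anxiety. Under the coding rule nearly all families already in treatment may answer alike, so name a method that tolerates separation, such as Firth logistic regression.
5. **Supportive analysis.** Repeat H1a and H1b in caregivers not already in treatment.

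The cost is one extra item, a wording change and a few lines in the SAP. The supportive sample is smaller. For the 17 participants with pre/post data, and anyone enrolled before the change, status would be retrospective and collected after exposure to the arm. Flag those answers and check them in a sensitivity analysis that omits them. If the full Treatment Seeking Evaluation already holds such an item, only the coding rule, index child and SAP text are needed.

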#### Secondary outcome measures:

3. Change From Pre-Presentation to Post-Presentation in Parent Engagement in Evidence-Based Services Questionnaire, Knowledge Subscale [Time Frame: pre-presentation; post-presentation (within 1 week after the presentation)]

The Parent Engagement in Evidence-Based Services Questionnaire, Knowledge subscale (PEEBS-K) assesses caregiver perceived understanding of how to seek evidence-based practice (Chang et al., 2019). Participants rate five items on a ranging

from 1 (*strongly disagree*) to 5 (*strongly agree*). Items are summed; higher scores indicate higher levels of perceived knowledge about seeking evidence-based practice.

4. Change From Pre-Presentation to Post-Presentation in Therapy Subjective Norms Questionnaire [Time Frame: pre-presentation; post-presentation (within 1 week after the presentation)]

The Therapy Subjective Norms Questionnaire is a six-item measure of caregiver perception of subjective norms for seeking therapy. It was modeled from previously used measures of subjective norms (Glanz et al., 2008; Park & Smith, 2007). Items are rated on a scale ranging from 1 (*strongly disagree*) to 7 (*strongly agree*). Items are summed; higher scores indicate more positive subjective norms about seeking therapy.

5. Change From Pre-Presentation to Post-Presentation in Caregiver Attitudes About Cognitive Behavioral Therapy [Time Frame: pre-presentation; post-presentation (within 1 week after the presentation)]

The Caregiver Attitudes about Cognitive Behavioral Therapy includes 18 strategies used in cognitive behavioral therapy for youth anxiety. Participants rate how helpful they believe each strategy would be for treating their child on a five-point scale ranging from 1 (*very unhelpful*) to 5 (*very helpful*). Items are summed; higher scores indicate more favorable attitudes.

6. Change From Pre-Presentation to Post-Presentation in Parents' Internalized Stigma of Mental Illness Scale [Time Frame: pre-presentation; post-presentation (within 1 week after the presentation)]

The Parents' Internalized Stigma of Mental Illness Scale (PISMIS) assesses caregiver perception of internalized stigma for having a youth with a mental illness (Zisman-Ilani et al., 2013). Participants rate each statement on a scale ranging from 1 (*strongly disagree*) to 4 (*strongly agree*); some items are reverse scored. Items are summed; higher scores indicate higher levels of family stigma.

### **Exploratory outcome measures:**

- 7. Change From Pre-Presentation to Post-Presentation in Barriers to Seeking Treatment [Time Frame: pre-presentation; post-presentation (within 1 week after the presentation)]

  The Barriers to Seeking Treatment questionnaire asks participants to indicate whether they agree with 21 potential barriers to treatment (Heeringa et al., 2004). A count of the total number of barriers will be used in analyses.
- 8. Change From Pre-Presentation to 3-Month Follow-Up in Barriers to Seeking Treatment [Time Frame: pre-presentation; 3-month follow-up]

The Barriers to Seeking Treatment questionnaire asks participants to indicate whether they agree with 21 potential barriers to treatment (yes/no; Heeringa et al., 2004). A count of the total number of barriers will be used in analyses.

9. Client Satisfaction Questionnaire [Time Frame: post-presentation (within 1 week after the presentation)]

The Client Satisfaction Questionnaire assesses participants' satisfaction with the presentation. Items are rated on scale ranging from 1 to 4. Items are summed; higher composite scores indicate greater program satisfaction.

10. Relatability Evaluation [Time Frame: post-presentation (within 1 week after the presentation)]

The Relatability Evaluation will be used to evaluate participants' impression of the presenter. Participants will rate each presenter (scale ranging from 1 to 5) on 10 items associated with aspects of key opinion leaders: relatable, likeable, similar, think similarly, similar beliefs, credible, trustworthy, understanding of the local community, familiar, and friendship. Items are summed; higher composite scores indicate that the presenter is more relatable.

11. Brief Revised Child Anxiety and Depression Scale-Parent Version [Time Frame: prepresentation]

The total anxiety scale (15 items) from the Brief Revised Child Anxiety and Depression Scale-Parent Version will be used to assess youth anxiety (Ebesutani et al., 2017). Participants rate items on a scale from 0 (*never*) to 3 (*always*). Items are summed; higher scores indicate higher levels of anxiety.

12. Demographics [Time Frame: pre-presentation]

A demographics questionnaire will assess caregiver and youth age, gender, race, ethnicity, and nativity; caregiver level of education, income, and religion; and youth health insurance status.

13. Content Checklist [Time Frame: during the 1.5 hour presentation]

A content checklist will assess the core components of the presentation, as well as presenter and audience member self-disclosure about experiencing receiving therapy for themselves or their child (yes/no). Self-disclosure will be considered to have been made if either the presenter or an audience member self-discloses about their experiences.

14. Qualitative Interview [Time Frame: 3-month follow-up]

A qualitative interview will ask participants about the following topics: (1) their perception of presenters; (2) ways in which the presenters affected their decision to seek treatment; (3) factors they considered when seeking treatment; (4) strategies they have used from the presentation; (5) their perception of exposure therapy; and (6) general ways that the mental health system could be improved to improve access to therapy.

